8.1 Ethical approval

The Chief Investigator has obtained approval from the Health Research Authority and Research Ethics Committee. The study must also receive confirmation of capacity and capability from Imperial College Healthcare NHS Trust before accepting participants into the study. The study will be conducted in accordance with the recommendations for physicians involved in research on human subjects adopted by the 18th World Medical Assembly, Helsinki 1964 and later revisions.

No human samples will be stored after they are taken for this study.

8.2 Consent

Consent to enter the study will be sought from each participant only after a full explanation has been given, an information leaflet offered, and time allowed for consideration. Sufficient time will be given to ask any questions about the study. Signed participant consent will be obtained for the collection of research blood samples and completion of a validated psychological tool. The right of the participant to refuse to participate without giving reasons will be respected.

After the participant has entered the study, the clinician remains free to deviate from the outlined pathway at any stage if he/she feels it is in the participants' best interest, but the reasons for doing so will be recorded. In these cases, the participants remain within the study for the purposes of follow-up and data analysis. All participants are free to withdraw at any time from the protocol treatment without giving a reason and without prejudicing further treatment.

8.3 Confidentiality

All patient derived data will be collected onto a paper proforma - primarily consent forms with a case report form (CRF). Patient identifiable data will at no point leave the hospital premises or be subject to access or viewing by anyone not involved with research being carried out. Code in the form of a three-digit number (e.g. 001) will be assigned to participants.

The study number will then be attached to the sheet as well as to the samples taken. The Clinical Research Fellow, [name], will keep a log which enables the matching of sample numbers to patient details. This log and all copies of all versions of the consent forms and the CRF will be stored within the study file. This is kept safely within the locked research filing area in the Early Pregnancy Unit, second floor, block D, Queen Charlotte's & Chelsea Hospital, Imperial College London, Hammersmith Campus, [name] and will only accessed when required by researchers directly involved in this study.

All potential identifiable participant data that requires electronic storage will be stored electronically on NHS approved computers, accessible only by a member of the study team or patients direct care team involved in the study via secure password.

All hard copies of data to be stored long term after the study has ended will remain filed securely within the Early Pregnancy Unit at Queen Charlotte's and Chelsea Hospital. All data stored electronically will be kept on an NHS approved computer's hard drive accessible only by responsible personnel involved in the study and will be password protected. This will be in the Early Pregnancy Unit, Queen Charlotte's & Chelsea Hospital, Imperial College Healthcare NHS Trust, Hammersmith Campus. At the end of the study, data will be archived at an Imperial College London archiving facility.

The Chief Investigator will preserve the confidentiality of participants taking part in the study and is registered under the Data Protection Act.

8.4 Indemnity

Imperial College London holds negligent harm and non-negligent harm insurance policies which apply to this study.

8.5 Sponsor

Imperial College London and Tommy's National Centre for Miscarriage Research at Imperial act as the main sponsors for this study. Funding for the fellows is provided by Imperial College Healthcare NHS Trust.

8.6 Adverse events

a. Definitions:

Adverse Event (AE): Any untoward medical occurrence in a patient or clinical study subject. *Serious Adverse Event (SAE):* Any untoward and unexpected medical occurrence or effect that:

- Results in death
- Is life-threatening refers to an event in which the subject was at risk of death at the time of the event; it does not refer to an event which hypothetically might have caused death if it were more severe
- Requires hospitalisation, or prolongation of existing inpatients' hospitalisation
- Results in persistent or significant disability or incapacity
- Is a congenital anomaly or birth defect

Medical judgement will be exercised in deciding whether an AE is serious in other situations. Important AEs that are not immediately life-threatening or do not result in death or hospitalisation but may jeopardise the subject or may require intervention to prevent one of the other outcomes listed in the definition above, will also be considered serious.

There are no additional risks to the patients participating in this study.

b. Reporting Procedures

All adverse events will be reported. Depending on the nature of the event the reporting procedures below will be followed. Any questions concerning adverse event reporting will be directed to the Chief Investigator in the first instance.

c. Non-serious AEs

All such events, whether expected or not, will be recorded.

d. Serious AEs

A SAE form will be completed and faxed to the Chief Investigator within 24 hours. However, relapse, death and hospitalisations for elective treatment of a pre-existing condition do not need reporting as SAEs.

All SAEs will be reported to the Chief Investigator who will determine if the event was:

- Related- resulted from the administration of any of the research procedures
- Unexpected- an event that is not listed in the protocol as an expected occurrence

Reports of related and unexpected SAEs will be submitted within 15 days of the Chief Investigator becoming aware of the event, using the NRES SAE form for non-IMP studies. The Chief Investigator will also notify the Sponsor of all SAEs.

Local investigators will report any SAEs as required by their Local Research Ethics

Committee, Sponsor and/or Research & Development Office.

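### Section 8.6 makes death a criterion for a serious adverse event and then exempts death from being reported as one

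*Combined protocol and SAP*

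**What the plan says.** Section 8.6a defines an SAE as an occurrence that is both untoward and unexpected and that meets one of five bulleted criteria. The first is "Results in death", with no limit by cause. The second and third are also relevant here: "Is life-threatening refers to an event in which the subject was at risk of death at the time of the event", and "Requires hospitalisation, or prolongation of existing" inpatient stay.

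Section 8.6b states that "All adverse events will be reported", refers the reader to the procedures that follow it, and adds that "Any questions concerning adverse event reporting will be directed to the Chief Investigator in the first instance".

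Section 8.6c requires non-serious events to be recorded. Section 8.6d covers serious ones. It opens with "A SAE form will be completed and faxed to the Chief Investigator within 24 hours". The next sentence is the exemption: "relapse, death and hospitalisations for elective treatment of a pre-existing condition do not need reporting as SAEs". It continues with "All SAEs will be reported to the Chief Investigator who will determine if the event was" related and unexpected, sets a 15-day limit for reports of events that are both, and has the Chief Investigator inform the Sponsor of every SAE. It closes by asking local investigators to report SAEs as their ethics committee, Sponsor or research office requires.

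**The concern.** The definition brings death in and the reporting rule takes it out. Two members of the team who both follow the protocol could handle the same death differently. One, working from 8.6a, sends the form within 24 hours. The other, working from the exemption in 8.6d, sends no SAE form.

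The later steps depend on that form or an equivalent report. Without it, the Chief Investigator may not judge whether the death was related or unexpected, the Sponsor may not be told, and a 15-day report, which applies only to a death that is both related and unexpected, may not be made.

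Relatedness cannot be dismissed in advance on the ground that the study only observes. Under 4.9 Method of study, patients in phase 2 receive the point-of-care result, so the study changes what information reaches the patient and when.

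**Working it through.** No arithmetic drives this point. The check sets the sentences of section 8.6 side by side and then follows particular events through them.

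**The rules as they apply to an untoward, unexpected death**

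| Place | Rule | Consequence for the death |
|---|---|---|
| 8.6a | Death is a criterion of seriousness | It is an SAE |
| 8.6b | Every adverse event is reported, by the procedures that follow | Reported, but the route depends on 8.6c or 8.6d |
| 8.6c | Non-serious events are recorded | Does not apply; the event is serious |
| 8.6d, first sentence | SAE form within 24 hours | Form required |
| 8.6d, exemption | Death need not be reported as an SAE | Form not required |
| 8.6d, later sentences | All SAEs go to the Chief Investigator and the Sponsor | Report required |

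The last three rows cannot all be followed for the same event.

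**How much of the definition the exemption touches**

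- Criteria bulleted in 8.6a: death, life-threatening event, hospitalisation, disability or incapacity, congenital anomaly or birth defect = 5.
- Named outright in the exemption: death = 1.
- Named in part: hospitalisation, only when elective and for a pre-existing condition = 1.
- Untouched: 5 − 1 − 1 = 3.

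**Three events traced through the text**

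1. *Death after an emergency admission, or after a recognised life-threatening phase.* The event also meets a criterion that the exemption does not name. On that ground it should still be reported, although the text does not say whether the exemption for death overrides the other criterion.
2. *Death with no earlier life-threatening or hospitalised phase.* Death is the criterion met, and it is the one exempted. Here the conflict is at its plainest. If the exemption is followed, 8.6d supplies no form, no deadline and no assessment, and 8.6c does not fit.
3. *Planned admission for a pre-existing condition.* The exemption narrows the hospitalisation criterion in a stated and limited way. This is not part of the concern.

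**Whether another reading removes the conflict**

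- *The qualifier about elective treatment governs the whole list.* It fits naturally only with hospitalisations. If it did extend to death, the conflict would be narrower, but 8.6a has no matching exception.
- *Only expected deaths are exempt.* The SAE definition covers only unexpected events, so a death that was truly expected would fall outside it anyway. But 8.6d does not limit the exemption in that way. It defines an unexpected event as one the protocol does not list as expected, and the available text contains no such list. It also gives the judgement of expectedness to the Chief Investigator once the event has been reported, which presupposes a report.

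**Relapse.** The term has no stated meaning for this cohort. That is an undefined term, not a contradiction of 8.6a.

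**The case against.** The strongest reply is that this is a general rule followed by an exception. Section 8.6a says what is serious, 8.6d says what is reported, and the exemption sentence opens with a word that signals an exception. A definition need not repeat every exception to reporting, and the elective-hospitalisation exemption works in just this way. This would be a full answer if the later sentences of 8.6d allowed for the exception. They do not: they require all SAEs to go to the Chief Investigator and the Sponsor. The conflict therefore lies within 8.6d as well as between 8.6a and 8.6d.

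A second reply is that the gap is nearly empty. Life-threatening is defined as being at risk of death at the time of the event, and most fatal events would fit that. This has force and reduces how often the wording would matter. It does not settle the case, because the text does not say whether a death that meets a second criterion is still exempt.

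Third, there are safeguards. Section 8.6b calls for all adverse events to be reported, questions go to the Chief Investigator, and local investigators have their own reporting duties. These lower the practical risk, and under 8.6b a death would still count as an adverse event to report. But 8.6b relies on the procedures below it, the invitation to ask helps only a reader who has noticed the conflict, and the local duty is itself framed in terms of SAEs.

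Fourth, the study carries little risk: questionnaires, a 1 ml research sample taken with routine blood, and at most two months of participation. That bears on frequency and priority. It does not decide which sentence a site should follow.

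**Conclusion.** The concern holds. For an untoward, unexpected death, section 8.6 both requires and waives reporting as an SAE, and no available sentence gives one rule precedence. The conflict is limited to unexpected deaths and is plainest where there was no earlier life-threatening or hospitalised phase. It names one of the five criteria outright and one in part.

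No count of affected events can be given, because the documents state no mortality rate. The defect is confined to safety-reporting wording and does not affect outcomes, sample size or analysis. It should be fixed: followed literally, the exemption would let a death bypass the SAE form and the relatedness assessment.

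Confidence is high, because every sentence needed is in section 8.6. Some text between 8.6d and section 8.7 was not available for this review, and nothing is assumed about it.

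**What to change.** Reconcile 8.6a and 8.6d. The simplest change is to delete death from the exemption in 8.6d, so that it covers only hospitalisations for elective treatment of a pre-existing condition and deaths follow the ordinary SAE procedure. In the same edit, delete relapse or say what it means in this cohort.

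The documents do not show what the sponsor intended. If some deaths were meant to be exempt, state the conditions in both 8.6a and 8.6d, and make the sentences that refer to all SAEs subject to them.

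The cost is a wording correction in 8.6d, with a matching line in 8.6a only if a limited exemption is kept. It has no effect on patients, visits, sample size or budget.
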